8.3.16. Maximum change from baseline of CHOP-INTEND score

The change from baseline of CHOP-INTEND score to maximum score at any visit up to 18 months of age will be presented at by overall and by subgroups, including subgroups, age at the time of treatment (≤ 4 months, > 4 months). An ANCOVA model with subgroup variable as the factor and baseline CHOP-INTEND score as a covariate, will be used to evaluate the comparability of the maximum change of CHOP-INTEND score between subgroups.

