1.2. Glossary of Definitions

Abbreviations list pertains to the SAP only.

| Abbreviation | Description |
|-----------------|--|
| AE | Adverse Event: Any untoward medical occurrence in a clinical investigation subject which does not necessarily have a causal relationship with the drug or device under study. |
| Age | For a given event, age will be expressed in months and rounded to one decimal place. A month is standardized to a period of 30 days. Age at Event = (Date of Event – Date of Birth + 1)/ 30. Age at Dosing = (Date of Gene Therapy Infusion – Date of Birth + 1)/ 30. |
| Baseline | Baseline, e.g., in terms of baseline laboratory values, vital signs, or physical exam results, refers to a measurement or evaluation made prior to initiation of gene therapy infusion. If there are multiple measurements prior to the initiation of gene therapy infusion, only the latest measurement will be considered as baseline for analysis purposes. |
| BiPAP | Bilevel Positive Airway Pressure, a form of non-invasive mechanical pressure support ventilation. |

| Abbreviation | Description |
|------------------------------|---|
| CHOP-INTEND | Children’s Hospital of Philadelphia Infant Test of Neuromuscular Disorders, a 16-item motor function assessment validated for use in infants with spinal muscular atrophy. |
| Day 1 | The day of the gene therapy treatment. |
| Dose | Total vector genome administrated (in vg /patient weight on Day – 1(kg)). |
| MedDRA | Medical Dictionary for Regulatory Activities is a medical terminology used to classify adverse event information associated with the use of biopharmaceuticals and other medical products. |
| CTCAE | Common Terminology Criteria for Adverse Events version 4.03. The CTCAE is descriptive terminology, involving a severity scale, which is used for AE reporting in particular for unique patient populations. It is a subset of MedDRA terminology. |
| Permanent Ventilation | Requirement of ≥ 16 -hour respiratory assistance per day (includes BiPAP) continuously for ≥ 14 days in the absence of an acute reversible illness, excluding perioperative ventilation. |
| PNCR | Pediatric Neuromuscular Clinical Research Network |
| Study Day | For any event of interest, Study Day = calendar date of event – calendar date of gene transfer +1. Day 1 is the Study Day of the gene transfer and any events occurring on the same calendar day as the gene transfer. |

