^a All post-treatment visits will be relative to the date on which gene replacement therapy ("dose") is administered until the patient is 14 months of age, after which all visits will be relative to the patient's date of birth. Note: Depending on the patient's age at dosing, the duration of participation at the end-of-trial visit can vary from approximately 12 months (baby dosed at approximately 6 months of age) to approximately 18 months (baby dosed near birth "0 months of age").

A schedule of trial assessments is provided in Section 3.5.1.

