6.7. Subgroups

Two subgroups based on age at dosing (study day 1) will be assessed in the selected analysis (developmental milestones and statistical modeling parts):

- Patients with age at dosing (study day 1) \leq 4 months (120 days)

- Patients with age at dosing (study day 1) > 4 months (120 days).

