8.3.14. Proportion of Patients that Achieve Ability to Walk Alone

The ability to walk alone is defined by WHO development milestones and will be based upon the maximum function achieved at any time point up to 18 months of age.

The numbers and percentages of patients who achieve ability to walk alone by the final visit will be presented by overall and by subgroups, including subgroups, age at the time of treatment (≤ 4 months, >4 months). The observed proportion achieving ability to walk alone during the observation period will be compared to zero using a 1-sided Exact Binomial Test, along with the corresponding 97.5% confidence intervals. To make computation of the p-value possible, the value of 0.1% will be used in place of a literal zero.

8.3.15. Improvement of Raw Score and Scaled Score using Bayley Scales of Infant and Toddler Development (Version 3), Fine and Gross Motor Function Subtests

Descriptive statistics for change from baseline in Fine and Gross motor function raw and scaled scores will be presented at each Study Day based visit, including mean, standard deviation, median, minimum, and maximum values.

Descriptive statistics for change from baseline in Fine and Gross motor function raw and scaled scores will also be presented at each Age Based visit, including mean, standard deviation, median, minimum, and maximum values.

The change from baseline of Bayley raw score to maximum score at any visit will be presented at by overall. An ANCOVA model with subgroup variable, as the factor and baseline Bayley score as a covariate, will be used to evaluate the comparability of the maximum change of Bayley score between subgroups.

The change from baseline will be analyzed by using mixed model with repeated measurement (MMRM). The model will include the change from baseline as the dependent variable, and fixed effects of subgroup, visit, and a covariate of baseline, age at baseline, and interactions of subgroup*visit, baseline*visit. A Toeplitz covariance structure will be assumed initially to model the within-patient errors; however, if the covariance structure results in non-convergence, the structure of compound symmetry will be used. The mean change from baseline (%), least squares (LS) means, differences between LS means, a 95% 2-sided CLs for each difference and the p-values from model effects will be reported for each scheduled visit through Month 18.

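### The subgroup ANCOVA on maximum CHOP-INTEND change mixes response to treatment with length of observation, because age at dosing sets how long each infant is followed

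*SAP*

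**What the plan says.** SAP 6.7 states: "Two subgroups based on age at dosing (study day 1) will be assessed in the selected analysis". The cut is at 120 days, the older group being "Patients with age at dosing (study day 1) > 4 months (120 days").

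SAP 8.3.16 defines the outcome as "The change from baseline of CHOP-INTEND score to maximum score at any visit up to 18 months of age" and the model as "An ANCOVA model with subgroup variable as the factor and baseline CHOP-INTEND score as a covariate". Its stated purpose is that it "will be used to evaluate the comparability of the maximum change of CHOP-INTEND score between subgroups". No margin or interval is given. SAP 8.3.15 plans the same kind of ANCOVA for Bayley, which "will be used to evaluate the comparability of the maximum change of Bayley score between subgroups". For Bayley it adds an MMRM with visit and subgroup-by-visit terms, reporting LS-mean differences and 95% limits at each visit. No such model is specified for CHOP-INTEND.

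The SAP recognises that follow-up depends on age at dosing. The note to Figure 1 in SAP 3.5 says participation "can vary from approximately 12 months (baby dosed at approximately 6 months of age) to approximately 18 months" for an infant dosed near birth.

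**The concern.** The grouping variable also determines planned follow-up: time observed is 18 months of age minus age at dosing. The outcome is a maximum, which can only stay level or rise as more visits are added. A model with baseline score as its only covariate cannot separate a better response from a longer period in which to reach a high score.

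Any bias favours the younger group. Protocol 5.5 already expects earlier treatment to do better, so a spurious difference would be easy to believe. In the other direction, about 30 infants give little information on a subgroup difference, so a non-significant result says little about comparability.

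**Working it through.** **Inputs.** A month is 30 days (SAP 1.2: "A month is standardized to a period of 30 days"). Eighteen months of age is 540 days, and final values are accepted to day 570 (SAP 6.2.3). Dosing is before 180 days of age (SAP 5.2). The 18-month visit window is 0 to +14 days (SAP 3.5). Enrolment is up to 30 (SAP 3.7). CHOP-INTEND testing stops after three consecutive scores of 58 or more (Protocol 11.2.3).

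**1. Reproduce the SAP's participation range.** Follow-up = (540 − age at dosing)/30.
- Dosed at day 1: 539/30 = 17.97 months.
- Dosed at day 179: 361/30 = 12.03 months.

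Both agree with the SAP's figures of about 18 and about 12 months.

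**2. Follow-up at the subgroup cut.**
- Dosed at day 120: 540 − 120 = 420 days = 14.00 months.
- Dosed at day 121: 540 − 121 = 419 days = 13.97 months.

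Scheduled follow-up is therefore 14.0 to about 18.0 months in the younger group and 12.0 to 13.97 months in the older. Scheduled post-dose CHOP-INTEND assessments number about 17–20 (dosed at day 120 back to day 30) against 16–17.

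**3. How firm the line is.** With the +14-day window an infant dosed at day 121 can reach 554 − 121 = 433 days, and at the 570-day limit 449 days. The Efficacy Completers population (SAP 5.4) also includes deaths and some discontinuations, so an early-dosed infant can fall below 420 days.

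**4. Size of the bias if scores still rise late.** The documents give no trajectory or SD, so everything here is assumed. With dosing ages uniform on 30–120 and 121–179 days, the mean gap in follow-up is (121 + 179)/2 − (30 + 120)/2 = 150 − 75 = 75 days, or 2.5 months. The spurious difference should be near late slope × 2.5.

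A simulation of the SAP's ANCOVA used the same response by time since dosing in both groups: +15 points over 6 months, then a late slope. Baseline mean was 30, visit SD 2, with 15 infants per group, 1,500 trials per row and no stopping rule.

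| Late slope (points/month) | Slope × 2.5 | Simulated difference, younger minus older | Rejection, between-child SD 4 | Rejection, SD 8 |
|---|---|---|---|---|
| 0 | 0 | 0.3 | 5.9% | 5.5% |
| 0.5 | 1.25 | 1.1–1.2 | 12.1% | 6.6% |
| 1 | 2.5 | 2.4–2.5 | 33.2% | 11.1% |
| 1.5 | 3.75 | 3.7–3.8 | 59.1% | 22.0% |

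A 20/10 split gave similar results. The last row should not be relied on. Its mean score at Month 14 is already 30 + 15 + 1.5 × (14 − 6) = 57, so the stop at 58 would cut later gains.

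A second simulation used linear gains of 1–2 points per month from dosing (between-child slope SD 0.3–0.7, 15 per group, dosing ages uniform on 0.5–4 and 4–6 months). Rejection was 19–35%, with a spurious difference of 2.8–5.6 points.

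Adding the stopping rule, with assumed baseline means of 32–36:
- At 2 points per month the difference falls from 5.5 to 1.7–2.6 points, and rejection from about 27% to 12–16%.
- At 1 point per month (slope SD 0.3) the rule alone changes little (35% to 32–33%).
- With the rule and a between-child response SD of 6, rejection across 1–2 points per month is about 14–18%.
- With an early plateau (time constant 4 months), rejection is about 7% without the rule and 5–6.5% with it.

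Limiting the maximum to Month 12 returned rejection to about 5% in the linear scenarios. That result depends on response being a function of time since dosing only.

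**5. What a non-significant result would show.** The half-width of the 95% CI, in SD units, is t × √(1/n₁ + 1/n₂):
- 15/15: 2.052 × 0.365 = 0.75
- 10/20: 2.052 × 0.387 = 0.80
- 12/13: 2.074 × 0.400 = 0.83

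Power for a true difference of 0.5 SD (an arbitrary reference value) is 26%, 24% and 22% respectively.

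**The case against.** Four points on the other side carry weight.

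- **The question is coherent.** The trial's motor endpoints are indexed by age. Maximum gain by 18 months of age is a legitimate total-effect question, in which longer time since dosing is part of what earlier dosing provides. Age equals age at dosing plus time since dosing, so the three cannot all be equalised. This stands, and it is why the planned ANCOVA should be kept and labelled for what it measures.
- **The size is uncertain.** Phase 1 gains are described as sustained (Protocol 5.4), which does not establish growth after Month 12, and the stopping rule limits late gains. The upper figures (35%, 5.6 points) come from scenarios without that rule or wider between-child variation.
- **Bayley is largely covered.** Its MMRM already gives visit-aligned subgroup differences with intervals. For CHOP-INTEND only summaries by visit and by age are planned, which do not replace a subgroup model.
- **Low precision is common to any subgroup comparison of this size.** This is true, and it is a reason to report an interval.

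A reader might infer that the two groups' follow-up never overlaps. That holds only for scheduled follow-up (step 3). A reader might also infer that the SAP will declare comparability from a non-significant test. It does not say so; it states a purpose and leaves the decision rule open.

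**Conclusion.** The point holds for SAP 8.3.16. The subgroup difference in maximum CHOP-INTEND change combines response with length of observation, and favours infants dosed at 120 days or younger if scores still rise after about Month 12.

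On assumed gains of 1–2 points per month, with no true difference at equal time since dosing, the false-positive rate is about 12–35%. With the stopping rule and larger between-child variation it is about 12–18%, and the spurious difference with that rule is about 2–3 points. With an early plateau the effect is small. These are ranges under stated assumptions and do not estimate what this trial will show.

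It would be wrong to infer that the trial's efficacy conclusions are in doubt. The ANCOVA is exploratory and lies outside the testing hierarchy in SAP 8.4; the primary and secondary analyses do not use it. The change is a low-cost improvement to how the effect of age at dosing is reported.

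**What to change.** In SAP 8.3.16, beside the existing ANCOVA, add one of:
- the same ANCOVA on the maximum change over a common period since dosing, using all visits up to study day 374 (the end of the Month 12 window in SAP Table 4); or
- a visit-aligned MMRM like the one in 8.3.15.

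Base any statement about response by age at dosing on the added analysis. Describe the ANCOVA to 18 months of age as including longer observation in the younger group. Replace the wording about judging comparability with estimation of the LS-mean difference and its 95% CI, and state that p > 0.05 is not evidence of comparability. For Bayley, base the subgroup statement on the MMRM already planned. That model also carries age at baseline, which overlaps with the age subgroups, so its subgroup difference needs to be read with that in mind.

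**Cost.** SAP wording and one derived variable from data already collected. There are three limits to state:
- Scores after Month 12 in early-dosed infants do not enter the common-period comparison, though they remain in the existing analysis.
- At equal time since dosing the groups differ in age: at Month 12, about 12–16 months (dosed at 0–4) against about 16–18 (dosed at 4–6).
- An infant dosed near 180 days with a late final visit contributes only to about Month 11. For example, dosed at day 178 and seen at day 554 is study day 554 − 178 + 1 = 377, past the window.

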8.3.17. Achievement of Selected Threshold Scores on CHOP-INTEND

8.3.17.1. Proportion of Patients Achieving CHOP-INTEND Score ≥ 40

The numbers and percentages of patients who achieve CHOP-INTEND score ≥ 40 by the final visit will be presented by overall and by subgroups, including subgroups, age at the time of treatment (≤ 4 months, > 4 months). The observed proportion achieving CHOP-INTEND score ≥ 40 during the observation period will be compared to zero using a 1-sided Exact Binomial Test, along with the corresponding 97.5% confidence intervals. To make computation of the p-value possible, the value of 0.1% will be used in place of a literal zero. Patients with baseline scores ≥ 40 will not be considered in the proportional analysis.

8.3.17.2. Proportion of Patients Achieving CHOP-INTEND Score ≥ 50

The numbers and percentages of patients who achieve CHOPINTEND score ≥ 50 by the final visit will be presented by overall and by subgroups, including subgroups, age at the time of treatment (≤ 4 months, > 4 months). The observed proportion achieving CHOP-INTEND score ≥ 50 during the observation period will be compared to zero using a 1-sided Exact Binomial Test, along with the corresponding 97.5% confidence intervals. To make computation of the p-

value possible, the value of 0.1% will be used in place of a literal zero. Patients with baseline scores ≥ 50 will not be considered in the proportional analysis.

8.3.17.3. Proportion of Patients Achieving CHOP-INTEND Score ≥ 58

The numbers and percentages of patients who achieve CHOP-INTEND score ≥ 58 by the final visit will be presented by overall and by subgroups, including subgroups, age at the time of treatment (≤ 4 months, >4 months). The observed proportion achieving CHOP-INTEND score ≥ 58 during the observation period will be compared to zero using a 1-sided Exact Binomial Test, along with the corresponding 97.5% confidence intervals. To make computation of the p-value possible, the value of 0.1% will be used in place of a literal zero. Patients with baseline scores ≥ 58 will not be considered in the proportional analysis.

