14.1.1.1.3. Exploratory Endpoints

For the following exploratory efficacy endpoints, a Responder will be defined as a patient who demonstrates achievement of the endpoint at any post-procedure visit up to and including the 18-month trial visit.

1. Proportion of patients that achieve the ability to hold head erect without support as defined by BSIDv03 Gross Motor Subtest Item #4 ([Appendix 3](#) and [Appendix 4](#)) [39].
2. Proportion of patients that achieve the ability to roll over as defined by BSIDv03 Gross Motor Subtest Item #20 ([Appendix 3](#) and [Appendix 4](#)) [39].
3. Proportion of patients that achieve functional independent sitting for at least 30 seconds as defined by BSIDv03 Gross Motor Subtest Item #26, ([Appendix 3](#) and [Appendix 4](#)) [39].
4. Proportion of patients that achieve the ability to stand with assistance for at least 2 seconds as defined by BSIDv03 Gross Motor Subtest Item #33 ([Appendix 3](#) and [Appendix 4](#)) [39].
5. Proportion of patients that achieve the ability to crawl forwards on hands and knees for a distance of at least 5 feet as defined by BSIDv03 Gross Motor Subtest Item #34 ([Appendix 3](#) and [Appendix 4](#)) [39].
6. Proportion of patients that achieve the ability to pull to standing as defined by BSIDv03 Gross Motor Subtest Item #35 ([Appendix 3](#) and [Appendix 4](#)) [39].
7. Proportion of patients that achieve the ability to walk with assistance as defined by BSIDv03 Gross Motor Subtest Item #37 ([Appendix 3](#) and [Appendix 4](#)) [39].
8. Proportion of patients that achieve the ability to stand alone for at least 3 seconds as defined by BSIDv03 Gross Motor Subtest Item #40 ([Appendix 3](#) and [Appendix 4](#)) [39].
9. Proportion of patients that achieve the ability to walk at least 3 steps without support as defined by BSIDv03 Gross Motor Subtest Item #42 ([Appendix 3](#) and [Appendix 4](#)) [39].

10. Proportion of patients that achieve the ability to crawl as defined by WHO Motor Developmental Milestones ([Appendix 5](#)) [38].
11. Proportion of patients that achieve the ability to stand with assistance as defined by WHO Motor Developmental Milestones ([Appendix 5](#)) [38].
12. Proportion of patients that achieve the ability to stand alone as defined by WHO Motor Developmental Milestones ([Appendix 5](#)) [38].
13. Proportion of patients that achieve the ability to walk with assistance as defined by WHO Motor Developmental Milestones ([Appendix 5](#)) [38].

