3.7. Determination of Sample Size

The current trial will enroll up to 30 patients. At least 25 symptomatic patients, the ITT population, will have biallelic deletion mutations of *SMN1*, two copies of *SMN2* and without the genetic modifier (c.859G>C), ensuring a reasonably robust safety database at the end of the study. The trial power is based upon efficacy analysis of the ITT population.

Based upon widely cited natural history of the disease (Pediatric Neuromuscular Clinical Research Network [PNCr]) [*Neurol.* 2014; 83(9):810-817], it is expected that no patients in this population would be expected to attain the ability to sit without support or accomplish other milestones (rolling over, standing, walking) prior to reaching 18 months of age. Assuming that the true response rate for the primary endpoint is actually zero (or as low as 0.1%) in the population of interest of the historical control, the primary efficacy endpoint hypothesis is:

$$H_0: p_{AVXS-101} = 0.1\%$$

versus the alternative

$$H_a: p_{AVXS-101} > 0.1\%,$$

where p is the proportion of functional independent sitting for at least 10 seconds up to and including the 18 month of age trial visit.

Based upon preliminary results from the ongoing Phase 1 clinical trial AVXS-101-CL-101, at least 50% of treated symptomatic patients with two copies of *SMN2* and without the genetic modifier (c.859G>C) are expected to achieve the primary efficacy endpoint of sitting without support for at least 10 seconds up to and including the 18 month of age trial visit. With the assumption for the true response rate of AVXS-101 being in the range of 20% - 50%, a sample size of 25 patients would provide power of greater than 95% to detect a significant difference with $\alpha = 0.025$ using a 1-sided exact test for a binomial proportion.

The secondary efficacy endpoint hypothesis:

$$H_0: p_{AVXS-101} = p_{PNCR}$$

versus the alternative

$$H_a: p_{AVXS-101} \neq p_{PNCR}$$

where p is the proportion of patients surviving at 14 months of age.

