6. GENERAL ASPECTS FOR STATISTICAL ANALYSIS

6.1. General Methods

All hypothesis testing will be conducted at one-sided with significance level $\alpha=0.025$ or two-sided, at significance level $\alpha=0.05$, as appropriate. Categorical measures, such as percent surviving event-free, will be summarized using count and percentages.

Continuous data, such as CHOP-INTEND scores, will be summarized using count, mean, median, standard deviation (SD), minimum, and maximum. For continuous data specified to be analyzed using parametric procedures, non-parametric procedures will be used if assumptions of parametric tests are not met.

Summary tables, listings, and figures, and statistical analyses will be done using SAS version 9.3 or higher. The primary and secondary efficacy analyses will be conducted on the ITT population. Safety analyses will be conducted on the Safety population.

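### The exploratory test of CHOP-INTEND ≥ 40 uses a 0.1% null that the documents support only for motor milestones, so score variation in a few infants just below 40 can make it significant without a treatment effect

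*SAP*

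**What the plan says.** SAP 8.3.17.1 takes the infants who score 40 or more on CHOP-INTEND and says that this proportion "during the observation period will be compared to zero using a 1-sided Exact Binomial Test". The null value is explained only by convenience: "To make computation of the p-value possible, the value of 0.1% will be used in place of a literal zero". SAP 6.1 sets the level: "All hypothesis testing will be conducted at one-sided with significance level" 0.025.

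The one entry restriction is "Patients with baseline scores ≥ 40 will not be considered in the proportional analysis". An infant entering at 38 or 39 is therefore kept.

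Protocol 14.1.1.1.3 supplies the counting rule for the exploratory endpoints: "a Responder will be defined as a patient who demonstrates achievement of the endpoint at any post-procedure visit". Neither document asks for a repeat score or a minimum gain. Protocol 11.3 sends milestone videos to an independent central reviewer but makes no such provision for CHOP-INTEND scores.

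The case for a near-zero untreated rate is in SAP 3.7. It says natural history gives no expectation that these infants would sit unsupported or "accomplish other milestones (rolling over, standing, walking) prior to reaching 18 months of age". CHOP-INTEND is not mentioned there.

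SAP 8.3.16 summarises "The change from baseline of CHOP-INTEND score to maximum score at any visit up to 18 months of age". SAP 8.4 limits the testing hierarchy to the primary and secondary endpoints.

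**The concern.** A milestone that untreated infants never attain can reasonably be tested against a rate close to zero. A 16-item sum score is different. It varies between visits with the infant's state and the scoring, and SAP 4.2.1 itself describes an optimal behavioural state for testing. An infant whose true score stays a little below 40 has a new chance of recording 40 at every visit, and a single success counts.

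The null of 0.1% applies to the whole follow-up of an infant, not to one visit. If a few infants enter just under 40, it may be wrong by orders of magnitude, and the test needs only one or two of them to cross. At stake is an exploratory p-value that would be read as evidence of motor benefit, when the test cannot tell a treated responder from a stable infant near the cut-off.

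**Working it through.** **The plan's own figure.** SAP 3.7 claims power above 95% for this same test (null 0.1%, one-sided 0.025) on the primary endpoint, with n = 25 and a true rate of 20% to 50%.
- P(at least 1 responder | n = 25, 0.1%) = 1 − 0.999^25 = 0.0247, so one responder is significant.
- Power at 20% = 1 − 0.8^25 = 0.9962, and at 50% it exceeds 0.9999. The claim is reproduced.

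**Critical count for ≥ 40.** The one-responder p-value is 1 − 0.999^n.
- n = 20: 0.0198. n = 25: 0.0247. n = 26: 0.0257. n = 30: 0.0296.
- One crosser is therefore enough for n ≤ 25, and two are needed for n = 26 to 30 (two at n = 30: p = 0.0004).
- Up to 30 infants are planned. Removing those with baseline ≥ 40 moves n towards the one-crosser range.

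**Number of looks.** The schedule (Days 7, 14, 21, 30, 60 and 90, then monthly to 18 months of age) gives about 16 to 21 post-dose scores by age at dosing, and 18 for an infant dosed at 90 days.

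**One infant.** Let d be the points below 40 and s the visit-to-visit SD, with independent errors and no true change. Then P(at least one crossing in 18 visits) = 1 − Φ(d/s)^18. The documents give neither d nor s, so both are assumptions:

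| s | d = 2 | d = 3 | d = 5 |
|---|---|---|---|
| 1 | 0.339 | 0.024 | <0.001 |
| 2 | 0.955 | 0.712 | 0.106 |
| 3 | 0.995 | 0.955 | 0.586 |

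Rounding scores to whole points lowers the effective threshold to 39.5, which raises the value at d = 3, s = 2 from 0.71 to 0.87. With an assumed decline of 1 point a month (unrounded), that value falls to 0.148.

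For 0.1% to be true over 18 visits, the per-visit chance must be at most 1 − 0.999^(1/18) = 0.0056%. That is a true score about 3.9 s below 40.

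**Whole trial.** Simulation with 28 infants, 18 visits, whole-point scores, no true change and infants with baseline ≥ 40 removed. Entries are the percentage of trials with a significant result, and repeat runs agree to within about two percentage points:

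| Baseline mean/SD | s = 1 | s = 2 | s = 3 |
|---|---|---|---|
| 30/8 | 65 | 93 | 99 |
| 30/5 | 26 | 75 | 97 |
| 25/8 | 15 | 45 | 76 |
| 25/5 | 0.4 | 6 | 29 |

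With a decline of 1 point a month:
- 30/8 with s = 2 gives about 67%.
- 25/8 with s = 1 gives about 3.5%.
- 25/5 gives 0%, under 1% and about 5% for s = 1, 2 and 3.

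With an error correlation of 0.5 between visits and no decline, 30/8 with s = 2 gives 91%.

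**Would a confirmation visit repair the test?** At 30/8, s = 2, requiring ≥ 40 at two consecutive visits cuts noise-only achievers from 12.6% to 5.6%. The test against 0.1% still fires in 65% of trials, so the null is the main fault.

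**Maximum change (8.3.16).** With no true change, the best of 18 scores exceeds baseline in 87% to 93% of infants, by 1.8 to 5.5 points on average for s = 1 to 3.

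**The case against.** The strongest reply is that the size rests wholly on assumed inputs. The documents give no baseline mean or SD, no visit-to-visit SD and no rate of decline, and some plausible settings show no inflation at all. An unchanging score also sits badly with untreated SMA Type 1: Protocol 11.2.3 describes the scale as tracking decline, and Protocol 5.1 describes progressive weakness. This stands. It limits the claim to what can happen.

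The decision impact is also limited. The endpoint is exploratory, and the count, percentage and 97.5% interval are planned anyway. In Phase 1, 11 of 12 Cohort 2 infants reached even 50 (Protocol 5.4). A result like that is far from a noise-only 12.6%, whatever the p-value. This stands too, but it argues for relying on the proportion and interval, not for keeping the test.

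Some stronger readings are tempting but not supported:
- That crossing is certain for any infant near 40. At d = 3 and s = 1 the chance is 0.024.
- That the SAP expects baselines around 40 because it excludes those already there. The same sentence is repeated for ≥ 50 and ≥ 58, so it shows only that such baselines are allowed.
- That 8.3.16 yields a false efficacy p-value. It has no test against zero, and its ANCOVA compares subgroups.

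**Conclusion.** The concern holds as a statement about validity, without a single figure for its size. The 0.1% null in SAP 8.3.17.1 has no stated support for a CHOP-INTEND threshold. Under the any-visit rule, one or two infants near 40 are enough for significance. The documentary elements and the critical counts are exact. The false-positive rate is not: about 0.4% to 99% with no true change across the settings examined, against a nominal 2.5%, and lower with natural decline or correlated errors. It is negligible if all infants enter about 4 visit SDs or more below 40.

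A reader might infer that the trial's efficacy conclusions are compromised. They are not, because this test lies outside the primary-secondary hierarchy. The fault is one exploratory p-value that cannot support the inference it invites.

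**What to change.** In SAP 8.3.17.1, delete the exact binomial test against 0.1%. Keep the number, the percentage and the confidence interval already planned there, and state that the interval is exact.

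Two optional additions would help the reader and need no new data:
- As a supportive sensitivity summary, the proportion scoring ≥ 40 at two consecutive scheduled visits. It should not replace the any-visit proportion, because Protocol 14.1.1.1.3 defines that endpoint.
- Beside the maximum change in 8.3.16, the change from baseline to the 18-month value already defined in SAP 6.2.3, with a note that a maximum over many visits is biased upward. The maximum change is also protocol-defined and stays.

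The cost is one exploratory p-value and a short SAP edit. The optional items add one derived flag and one summary row.
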